9.3. Variables

Regardless of the coding system used in the database, different populations and subgroups of interest are defined as follows:

Treatment initiation with dulaglutide:

- any record of prescription of dulaglutide during the observation period without prior record of prescription of the same product in the available patient's history
- if no prior history is available to check the above criteria, the prescription is not considered as an initiation

Patients presenting with T2DM:

- with any recorded diagnosis code for T2DM
- or with any recorded treatment code for an ADM other than insulin
- or, with any recorded treatment code for insulin initiated at age >30 (defined as no record of insulin therapy during 6 months prior to first record of insulin treatment)
- or with any record of unspecified diabetes mellitus diagnosis at age >30 and without history of insulin therapy (defined as no record of insulin therapy during 6 months prior to first record of diabetes diagnosis),
- a sensitivity analysis will be conducted to determine the age threshold mentioned above (see section 9.7.3 Sensitivity analysis).

Patients with severe renal failure:

- with a recorded diagnosis of severe renal failure
- or with a recorded glomerular filtration rate (eGFR) value <30 ml/min/1.73 m²

Patients with hepatic disease:

- with a recorded diagnosis of any hepatic disorder

Patients with heart failure:

- with a recorded diagnosis of heart failure

Patients with severe gastrointestinal disease:

- with a recorded diagnosis of any of the following conditions:
 - cancer of the gastrointestinal tract,
 - diseases of the oesophagus,
 - active ulcer at the time of drug initiation (gastric, duodenal, gastro-jejunal, peptic ulcer of unspecified site),
 - active haemorrhagic gastritis, chronic atrophic gastritis, adult hypertrophic pyloric stenosis, obstruction of duodenum, and other motility disorders,
 - digestive fistula,
 - Crohn's disease, ulcerative colitis,
 - diverticular disease of the intestine,
 - severe vomiting, severe diarrhoea and severe constipation
 - motility disorders, including ileus, gastroparesis, et cetera,
 - infectious and inflammatory situations (appendicitis, cholecystitis, cholangitis).

Children and adolescents:

- Age < 18 at the time of treatment initiation
(subgroups of analysis: 0-4, 5-9, 10-14, and 15-17 years old).

Elderly:

- Age \geq 75 at the time of treatment initiation.

Pregnant and breastfeeding women:

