9.3.2. Collected variables

To assess the above subgroups and measurements of interest, several variables will be extracted from each database whenever available: demographics, medical history, treatment, clinical and clinical laboratory data on patients. These variables along with their corresponding International Classification of Disease, 10th version (ICD-10) codes are presented in this protocol (Table 9.3.2-1). For CPRD database, the corresponding Read codes will be specified in the statistical analysis plan (SAP).

Table 9.3.2-1. Variables, Subgroups and Measurements of Interest in Dulaglutide Initiators

Variable, subgroup or outcome/measurement	Definition and categories*
Patients demographics at initiation of dulaglutide use: Age Gender BMI categories, Countries	< 18, 18-44, 45-64, 65-74, ≥75 years Male or Female Weight (kg) / Height (cm) ² < 18.5, 18.5-25, 26-30, > 30 kg/m ² UK, Germany, Sweden (or Spain and France)
Co-morbidities , at initiation of treatment to identify the subgroups of interest: 
 • History of severe renal failure • Heart failure • Hepatic disease • Severe gastrointestinal disease • Children and adolescents • Elderly • Pregnant women • Breastfeeding women 	ICD-10 code N18.5, N18.5 ICD-10 codes I50, I11, I13 ICD-10 codes B18, K70-K77, C22 ICD-10 codes C15-C26 K22.0, K22.1, K22.2 -K22.6, K23-K28, K29.0, K29.4 K50, K51, K55, K57 Age < 18 (subgroups: 0-4, 5-9, 10-14, 15-17 years) Age ≥ 75 ICD-10 codes: A34, E23.0, F53, M83, O00-O99, O24.1, O24.3, O24.9, Z32-Z36, Z39 Z39.1
Lab tests values (if available): 
 • Haemoglobin A1c (HbA1c) • e-GFR • Serum Creatinine Urine albumin/creatinine ratio (UACR) 
 • LDL-C (LDL-cholesterol) • HDL-C (HDL-cholesterol) • AST/ALT • Bilirubin • Beta hCG 	Abnormal values: < 6.5%, ≥6.5% eGFR value < 30 ml/min/1.73 m ² < 120, ≥120 µmol/L or mg/dL (male) < 100, ≥100 µmol/L or mg/dL (female) UACR >30 mg/g: albuminuria present: < 1.6, ≥ 1.6 g/L < 0.35 g/L, ≥0.35 g/L ≤ 2 or > 2 times upper limit of the normal range < 2, >7mg/L Positive

Variables, Subgroups and Measurements of Interest

Variable, subgroup or outcome/measurement	Definition and categories*

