9.4.2. SIDIAP in Spain

The SIDIAP database contains information from 274 primary care centres in Catalonia, Spain, with a source population of 5.5 million patients which encompasses 80% of the total Catalan population. The SIDIAP aims to register all health information with research value in an anonymised database for every patient.

The Primary Care e-records (eCAP) database which contains information on primary care since 2000 is the basis of the source population in SIDIAP. Various external data sources can be linked to eCAP as required to provide a more complete picture of the cohort profile. In this study, it is proposed to use eCAP, Catalan Health Service Database (SIAP), Pharmacy Official Invoice Database, Primary Care Lab Database, and CMBD-AH to capture the parameters required in this study.

Table 9.4.2-1. Collectable Data in the Databases Linkable to SIDIAP

Variables	Source	Years available
Clinical (GP visits, referrals, vaccines, smoking, drinking, body mass index, blood pressure, spirometry, ICD-10 codes, etc.)	eCAP (Primary Care e-records)	>2000
Sociodemographics (date of birth, gender, country of origin)	SIAP (Catalan Health Service Database)	>2000
Drugs dispensed in community pharmacies	Pharmacy Official Invoice Database (subsidised drugs)	>2005
Lab tests (creatinine, HbA1c, et cetera.)	Primary Care Lab Database	>2006

Abbreviations: GP= general practitioner; HbA1c= haemoglobin A1c; ICD-10= International classification of disease, 10th version.

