9.4.5. Summary of Data Sources

The following table (Table 9.4.5-1) presents the expected data which could be provided from local databases.

Table 9.4.5-1. Data Availability per Database / Country

Data availability per country (local database)	France (FR-DA)	Germany (DE-DA)	Spain (SIDIAP)	Sweden (NPR and SPDR)	The UK (CPRD)
Demographics (age, gender)	Yes	Yes	Yes	Yes	Yes
Clinical parameters (height, weight, BMI,)	Yes	Yes	Yes	No	Yes
Physiological status: pregnancy breastfeeding women	Very limited	Very limited	Very limited	Very limited	Very limited
Date of consultation	Yes	Yes	Yes	Yes	Yes
Diagnosis	Yes ICD-10 codes	Yes ICD-10 codes	Yes ICD-10 codes	Yes ICD-10 codes	Yes READ codes
Prescribed drug characteristics (name, form, package, classification code)	Yes (ATC/EphMRA codes)	Yes (ATC/EphMRA codes)	Yes (ATC codes)	Yes (ATC codes)	Yes (associated medcodes)
Dosage	Yes	Yes	Yes	Yes	Yes
Duration exposure	Yes	Yes	Yes	Yes	Yes

Co-prescriptions	Yes	Yes	Yes	Yes	Yes
Treatment history	Yes	Yes	Yes	Yes	Yes
Biological test (HbA1c, cholesterol level, creatinine, ..)	Yes	Yes	Yes	No	Yes

Abbreviations: CPRD= Clinical Practice Research Datalink; DE-DA= Deutschland Disease Analyzer; FR-DA= France Disease Analyzer; HbA1c= haemoglobin A1c; ICD-10= International classification of disease, 10th version; NPR= National Prescription Registry; SIDIAP= The Information System for the Development of Research in Primary Care; SPDR= Swedish prescribed drug register.

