- Since it will not be possible to distinguish between patients that were appropriately prescribed dulaglutide monotherapy (ie, when diet and exercise alone did not provide adequate glycaemic control and the use of metformin was considered inappropriate due to intolerance or contraindications) and patients who were prescribed monotherapy inappropriately (i.e. did not meet these criteria), the number of patients found to be taking off-label first line dulaglutide will be an overestimate of the number of actual patients taking off label first line dulaglutide.
- Medication errors will be evaluated based on the time span between the first prescription and the next one. In a number of cases the next prescription will not be still captured in the database. These cases will be considered as missing data for the analysis of medication errors. Other sources of bias:
 - **Selection bias:** in some databases (for example, French and German DA) the sample of physicians are representative of the physicians in each country in terms of the stratification factors used to select the panel. However, it is not known whether the physicians who belong to the panel have the same prescription behaviour as the physicians who are not part of the panel, especially those who were invited to take part but refused. Similar considerations can be expressed for physicians who belong for a long time and physicians recently included in the panel. To control these biases as much as possible, the distribution of the strata in each data base will be compared to the distribution of strata of the corresponding physicians' population in the country. This limit does not apply to the Swedish cohorts because of their exhaustiveness.
 - **Misclassification bias:** Misclassification bias can result if study subjects are not categorised correctly with regards to exposure or selected patient characteristics. Since the data bases are fully anonymised, it is impossible to verify the information with source data. This bias cannot be controlled as there is no possibility to check the information in databases. For example, the definition of severe renal failure is based on eGFR. However, this value may not be recorded relevantly in the database. Consequently, there may be false negatives of severe renal failure, that is, those with this condition who are classified as not having the severe renal failure.

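### Severe renal failure is identified only from a recorded diagnosis or a recorded eGFR, so patients with creatinine alone are missed although creatinine, age and sex are extracted

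*Protocol*

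**What the plan says.** Section 9.3 gives two routes into the subgroup: "with a recorded diagnosis of severe renal failure", or an eGFR below 30 that has been recorded ("or with a recorded glomerular filtration rate (eGFR) value <30 ml/min/1.73"). For the diagnosis route, Table 9.3.2-1 lists "ICD-10 code N18.5, N18.5", which is one code printed twice.

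The same table collects laboratory values where available. Recorded eGFR is one row. Serum creatinine is another, split at 120 for men and 100 for women, with one cut-off printed for two units ("< 120, ≥120 µmol/L or mg/dL (male"). No text links the creatinine row to the renal subgroup. Age and sex are collected, and Table 9.4.5-1 shows them available in all five databases.

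On what the databases hold, Table 9.4.5-1 gives "Biological test (HbA1c, cholesterol level, creatinine" as present in France, Germany, Spain and the UK and absent in Sweden. Table 9.4.2-1 gives "Lab tests (creatinine, HbA1c, et cetera" for SIDIAP. Both lists are open-ended.

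Section 9.9.1, under misclassification, uses the recorded eGFR as its example: "However, this value may not be recorded relevantly in the database. Consequently, there may be false negatives of severe renal failure".

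**The concern.** Severe renal failure is the first population listed in the primary objective, and off-label use within it is part of the secondary objective. The laboratory route depends on whether an eGFR was stored, not on whether the patient's renal function was measured. Where a database holds creatinine without an eGFR, the plan has the information needed to classify the patient but does not use it.

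The diagnosis route cannot be relied on to recover these patients. Section 9.9.1 says that diagnoses will be missing for some patients, especially in primary care, and the code list has only the one repeated entry.

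The result is a reported frequency of use in severe renal failure that is too low, and a description of that subgroup that omits some of its members.

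**Working it through.** **Plan's own figures.** The protocol gives no figure for the size of the renal subgroup or for how completely it is captured. Its only computed figures are the sample sizes in Section 9.5.1, from n = p(1−p)z²/e² with p = 0.5 and z = 1.96. For e = 5, 3 and 10 points I obtain 384.1, 1067.1 and 96.0, against the stated 384, 1066 and 97. These agree apart from rounding, and this point does not change them.

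**Who is missed.** Setting the definition beside the variable list:

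| What the record holds | Section 9.3 as written | With eGFR calculated |
|---|---|---|
| Diagnosis code | in | in |
| Recorded eGFR below 30 | in | in |
| Creatinine implying eGFR below 30, no stored eGFR, no code | **out** | in |
| None of these | out | out |

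Only the third row changes. It is empty in Sweden, which has no laboratory results.

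**Does the existing creatinine row serve instead?** Take CKD-EPI 2009 without an ethnicity term as an assumed equation (the protocol names none) and read the cut-offs as µmol/L:

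eGFR = 141 × min(Scr/κ, 1)^α × max(Scr/κ, 1)^−1.209 × 0.993^age × 1.018 (if female)

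Here Scr is in mg/dL (µmol/L ÷ 88.4), κ = 0.7 (women) or 0.9 (men), and α = −0.329 or −0.411.

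- Creatinine at which eGFR = 30, age 70: about 150 µmol/L (woman) and 191 µmol/L (man).
- eGFR at the table's cut-offs, age 70: 49.1 for a woman at 100 µmol/L and 52.5 for a man at 120 µmol/L.
- Over ages 50 to 85, the cut-offs give eGFR of about 44–57 (women) and 47–60 (men).

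The dichotomised row therefore cannot stand in for the subgroup, and the protocol does not say that it should. The calculation needs the continuous creatinine value, its unit, and age in years.

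**How many?** Let N be initiators, π the true prevalence of severe renal failure, and m the share of true cases with creatinine alone (no stored eGFR, no code). Then missed = N × π × m, and the reported prevalence is π(1 − m). The protocol gives neither π nor m, so the values below are assumptions:

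| N | π | True cases | Missed, m = 10% | Missed, m = 30% | Missed, m = 50% |
|---|---|---|---|---|---|
| 1,000 | 1% | 10 | 1 | 3 | 5 |
| 1,000 | 3% | 30 | 3 | 9 | 15 |
| 1,000 | 5% | 50 | 5 | 15 | 25 |
| 100 | 1% | 1 | 0.1 | 0.3 | 0.5 |
| 100 | 3% | 3 | 0.3 | 0.9 | 1.5 |
| 100 | 5% | 5 | 0.5 | 1.5 | 2.5 |

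At π = 3% and m = 30%, 21 of 30 cases per 1,000 are found, so 2.1% is reported in place of 3.0%. In relative terms the loss equals m, whatever the prevalence. Because results are not pooled across countries or years, the rows for 1,000 should be read as rates, not as counts in one table.

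**The case against.** Several objections have weight.

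- **The limitation is disclosed.** Section 9.9.1 states the false negatives and their direction, and notes that laboratory values are incomplete. This stands: the bias was not overlooked. What remains is that an available partial remedy is unused.
- **Section 9.9.1 is not wrong.** A reader might infer that the protocol wrongly calls the renal false negatives uncontrollable. That sentence concerns misclassification in general, and its reason is that anonymised records cannot be checked against source. Renal failure follows as an example. Calculating an eGFR verifies nothing against source, so the sentence can stay.
- **eGFR may be held.** A reader might infer from the data-source tables that the databases store creatinine but not eGFR. Both lists are open-ended, Table 9.3.2-1 lists eGFR as its own variable, and the feasibility assessment in Section 9.5.2 will check the availability of each variable. How often creatinine stands alone is unknown.
- **Most of the bias would not necessarily go.** No figure supports saying that the calculation would remove most of it. Patients with neither value stay missed, and some with creatinine alone on the laboratory side already enter by diagnosis.
- **Comparability between countries is only partly helped.** No formal comparison is planned. Sweden gains nothing, so better capture elsewhere could widen its gap from the other countries.
- **The SAP could add the rule.** It may, but Section 9.7.5 bases the SAP on the protocol, and Section 9.3 fixes the criterion as a recorded value. That wording would have to change.

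The no-imputation statement in Section 9.9.1 is no obstacle: computing eGFR from a patient's own measured creatinine is a derivation, like BMI from weight and height.

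**Conclusion.** The point holds as a gap in the stated definition. Followed as written, Section 9.3 leaves out patients whose only evidence of severe renal failure is a creatinine value, and so under-counts a primary-objective population in any database where such patients exist.

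The size is unknown. The range of 1 to 25 per 1,000 initiators (0.1 to 2.5 per 100, the minimum for the smallest country) rests wholly on the assumed prevalence of 1–5% and the assumed 10–50% with creatinine alone. The documents do not show that the loss is large or that calculation would remove most of it. The change should be made before extraction because it is cheap and uses data already requested, not because a large bias has been demonstrated.

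**What to change.** 1. In Section 9.3, add a third route: eGFR below 30 calculated by one named equation, in adults, from the most recent serum creatinine on or before the index date and within a stated look-back window.
2. First settle the creatinine unit in Table 9.3.2-1, where one cut-off is printed for both µmol/L and mg/dL, and extract the continuous value with its unit. Check the repeated diagnosis code at the same time.
3. Report, per country, how many patients enter by diagnosis, by recorded eGFR and by calculated eGFR.
4. State that Sweden, if selected, rests on diagnosis codes alone and that its subgroup frequency is not comparable with the other countries.
5. In Section 9.9.1, keep the general sentence on source verification and add that the renal false negatives are partly reduced where creatinine is recorded.

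The cost is one derived variable, a unit check per database and a few lines of text. The sample size is unaffected. The downside is some false positives: an acute rise in creatinine can place a patient in the subgroup, and an equation without an ethnicity term is less exact for some patients. The look-back window limits the use of old values, and the counts by route let a reader see how much rests on the calculated values.

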PASS Information

Title	Utilisation of dulaglutide in European countries: A cross-sectional, multi-country and multi-source drug utilisation study using electronic health record databases.
Version identifier	Version 1.0
Date of last version	01 May 2016
EU PAS Register No:	Study not registered
Active substance	Dulaglutide (ATC code: A10BX)
Medicinal product(s):	Trulicity 0.75 mg solution for injection Trulicity 1.5 mg solution for injection
Product reference:	EU/1/14/956
Procedure number:	EMA/H/C/002825
Marketing authorisation holder(s)	Eli Lilly Nederland B.V.
Joint PASS	No
Research question and objectives	
The purpose of this study is to describe how dulaglutide is used among different patient groups in European countries.
 
Primary objective: To describe the frequency of dulaglutide use in the population and characterise by age, gender, main co-morbidities and main co-prescriptions overall and in the following subgroups of interest:
 
 ○ Populations of interest: 
 • Patients with severe renal failure • Patients with hepatic disease • Patients with heart failure • Patients with severe gastrointestinal disease • Children and adolescents <18 years of age • Elderly patients ≥75 years • Pregnant and breastfeeding women ○ Medication use : 
 • Medication errors • Off-label use 
Secondary objective: To describe the off-label use among each of the above populations of interest.

Country(-ies) of study	Several countries will be selected from the databases under consideration (France, Germany, Spain, Sweden and the United-Kingdom) based on the criteria described in the feasibility analysis (see Section 9.5.2).
Author	IMS Health [name], Medical director [name], Senior Medical writer and project lead

Approval Date: 07-Jun-2016 GMT

Marketing Authorisation Holder

Marketing authorisation holder (MAH)	Eli Lilly Nederland B.V.
MAH contact person	[name], Pharmacoepidemiologist Eli Lilly and Company

1. Table of Contents

Section	Page
1. Table of Contents.....	3
2. List of Abbreviations	7
3. Responsible Parties	9
4. Abstract	10
5. Amendments and Updates.....	14
6. Milestones.....	15
7. Rationale and Background	16
8. Research Question and Objectives.....	17
9. Research Methods.....	18
9.1. Study Design.....	18
9.2. Setting and Population.....	18
9.2.1. Setting.....	18
9.2.2. Inclusion Criteria	18
9.2.3. Population of Interest	18

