- Any record of pregnancy or breast feeding at the time of treatment initiation.

Patients with medication errors:

- Prescribed and/or administered > 1 dose per week of dulaglutide (6).
- The number of doses/week will be calculated by measuring the time span between the current prescription and the next one (in weeks) and dividing the number of injections prescribed in the current prescription by this time span. This number of doses/week will be used in the cross sectional study as an attribute of the prescription to assess the occurrence of medication errors as described above.

Patients with off-label use:

- Prescribed dulaglutide with no diagnosis of T2DM as defined above, at the beginning of this list of subgroups of populations.
- Prescribed dulaglutide with a diagnosis of T2DM as defined above and without a record of other ADMs during the 6-month baseline period, i.e. dulaglutide was prescribed as first-line therapy.

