9.4.1. Disease Analyzer in France and Germany

The IMS Disease Analyzer (DA) is a longitudinal patient database providing information from continuing physician and patient interactions on consultations, diagnoses and treatments. This database is available in France and Germany. Anonymous data are collected continuously through the medical software, allowing longitudinal follow-up of all the different visits of the same patient consulting the same general practitioner (GP) in the panel. The collected data include administrative (for example, insurance scheme, socioeconomic status), demographic (for example, age, gender, region), anthropometric (for example, height, weight, body mass index [BMI]), clinical (signs, symptoms and diagnoses according to ICD-10 classification), laboratory (lab results reported by the physicians) and therapeutic (EPHMRA/ATC class, molecule / brand name, dosage, route of administration) information. An update of the database is done monthly with a lag time of 6 weeks.

Comparisons with external data sources (for example, data from statutory health insurances) underline the validity and representativeness of the German DA in pharmacoepidemiological and pharmaco-economic studies (7).

The DA is currently used by the European Medicines Agency (EMA) as one of its resources for answering research questions.

DA in France:

The data collection is based on five different EHR applications used by 1200 GPs. The French database is representative in terms of GP distribution, patient profile, age group, and sex. It allows for a longitudinal follow-up of all the different visits of the same patient consulting the same GP in the panel. Due to the role of GPs as the first point of care in France, the loyalty of patients to GPs is very high and each GP provides a continuous follow-up of patients.

DA in Germany:

The German DA is based on patient records continuously collected from 2400 computerised practices (including 1400 GPs and 1000 specialists), using three different EHR application. The sample is designed to be representative of Germany (7).

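### Medication error is judged only from the gap to the next prescription, so over-frequent prescribing can be missed and a change of strength before supply ends is counted as an error

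*Protocol*

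**What the plan says.** Section 9.3 sets the criterion as "Prescribed and/or administered > 1 dose per week of dulaglutide". It covers two different things: what was prescribed and what was administered. One calculation then serves both. "The number of doses/week will be calculated by measuring the time span between the current prescription and the next one (in weeks"), and the rest of the rule is "dividing the number of injections prescribed in the current prescription by this time span". The result is to be used "as an attribute of the prescription to assess the occurrence of medication errors as described above".

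Section 9.9.1 restates the method for the start of treatment: "Medication errors will be evaluated based on the time span between the first prescription and the next one". Patients whose next prescription is not captured are set to missing for this outcome.

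Three other places matter:

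- The PASS Information table lists two strengths: "Trulicity 0.75 mg solution for injection Trulicity 1.5 mg solution for injection". The abstract plans analyses by strength prescribed.
- Table 9.4.5-1 marks dosage as expected in all five databases. Section 9.4.1 says that the French and German Disease Analyzer collects "therapeutic (EPHMRA/ATC class, molecule / brand name, dosage, route of administration) information".
- Table 9.3.2-1 has a weekly dose variable with categories 0.75, 1.5 and above 1.5 mg per week. Nothing links it to the medication-error definition.

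**The concern.** The ratio measures how soon the next prescription follows. It is not a measure of what the prescriber wrote, so the prescribed part of the definition has no measure of its own, although a dosage field is expected in every candidate database. The ratio also assumes that everything supplied was used by the date of the next prescription. That assumption fails when the next prescription replaces the current one with the other strength, because part of the first supply may be left unused.

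Medication error is one of the nine subgroups under the primary objective and part of the stated rationale. Its classification rule decides both the reported proportion and who is described in that column of the results table. Errors in the rule affect both.

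**Working it through.** **Inputs.** The rule is R = k / g, where k is the number of injections in the current prescription and g is the weeks to the next one. A patient is an error if R > 1 (Section 9.3) and missing if there is no next prescription (Section 9.9.1). No strength condition is stated. The protocol does not give k, so values of 2, 4, 8 and 12 are assumptions for illustration. The protocol gives no expected frequency of medication errors, so there is no figure of its own to reproduce.

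**Step 1: a prescription written for two doses per week.** R > 1 is the same as g < k. The written frequency is not in the formula, and only the timing of renewal decides.

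| k | Next prescription | R | Result |
|---|---|---|---|
| 4 | week 2 (the written schedule) | 4/2 = 2.0 | flagged |
| 4 | week 3 | 4/3 = 1.33 | flagged |
| 4 | week 4 | 4/4 = 1.0 | not flagged |
| 8 | week 4 (the written schedule) | 8/4 = 2.0 | flagged |
| 8 | week 6 | 8/6 = 1.33 | flagged |
| 8 | week 8 | 8/8 = 1.0 | not flagged |
| any | none captured | – | missing |

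The prescribing error is found if renewal follows the written schedule. It is missed once renewal is as slow as one injection per week or slower, and it is lost when there is no second prescription, even if the dosage on the first one shows it.

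**Step 2: one injection used per week, then a change to the other strength.**

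| k | Change at | R | Result |
|---|---|---|---|
| 2 | week 1 | 2/1 = 2.0 | flagged |
| 2 | week 2 | 2/2 = 1.0 | not flagged |
| 4 | week 1 | 4/1 = 4.0 | flagged |
| 4 | week 2 | 4/2 = 2.0 | flagged |
| 4 | week 3 | 4/3 = 1.33 | flagged |
| 4 | week 4 | 4/4 = 1.0 | not flagged |
| 12 | week 4 | 12/4 = 3.0 | flagged |
| 12 | week 8 | 12/8 = 1.5 | flagged |
| 12 | week 12 | 12/12 = 1.0 | not flagged |

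Every change before week k is flagged, although nothing in the data shows more than one dose in any week. A change at week k or later is not flagged. On the Section 9.9.1 wording the interval tested starts at the first prescription, so a change made during the first supply falls inside it.

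**Step 3: can the weekly dose variable stand in?** Two 0.75 mg injections give 2 × 0.75 = 1.5 mg per week, the same category as one 1.5 mg injection. Two 1.5 mg injections give 3.0 mg per week and would show in the top category, but that category does not feed the medication-error subgroup. The variable covers part of the gap at most.

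**The case against.** Several points can be made for the plan, and some of them stand.

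- *Over-frequent prescribing is not invisible.* A reader might infer that the rule has no sensitivity for prescribing errors. That is wrong: a two-per-week prescription renewed on its own schedule scores 2.0 and is flagged. The loss is confined to slow renewal and to patients without a second prescription.
- *Not every change of strength is flagged.* Only a change before supply ends is.
- *Dosage is not yet known to be usable.* Table 9.4.5-1 lists expected data, and Section 9.5.2 leaves the availability and validity of each variable to be checked. The table does not say whether dosage means prescribed frequency or only strength. The Swedish drug register covers dispensed drugs, and Section 9.9.1 says that doses in SIDIAP can only be estimated from dispensing. A direct measure may not be possible in every country.
- *Some of this is conceded.* Section 9.9.1 acknowledges the missing next prescription and the SIDIAP proxy. It does not mention change of strength or the unused dosage field.
- *The same-strength condition could be left to the SAP.* The SAP, which is not shown, may add it. The protocol nevertheless fixes the formula, and followed as written it misclassifies. The lack of a direct measure for prescribed frequency is a matter of definition and not of programming detail.

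A reader might also conclude that administration is recorded nowhere. The documents say that administered doses per week are unknown only for SIDIAP.

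**Conclusion.** The point holds in a limited form. The definition names prescribed frequency, but the only stated measure is the refill ratio, which can miss a prescription written for more than one dose per week and cannot assess one with no successor. The absence of a same-strength condition turns a change of strength before supply ends into a counted error.

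The direction of each effect is certain. The size is not. The documents give no pack size, no rate or timing of strength changes, and no rate of over-frequent prescribing. It is tempting to attach an inflation figure to the reported proportion, but any such figure would be purely hypothetical. The two effects also work in opposite directions, so even the net bias cannot be signed. What can be said is that each assessable patient whose tested interval ends in an early change of strength adds one flag that the data do not support.

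This does not threaten the study as a whole. It does make one primary subgroup hard to interpret, and it should be settled before data collection.

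**What to change.** 1. Add to the feasibility assessment a check, per database, of whether recorded dosage gives the prescribed frequency and how complete it is.
2. Where it does, classify prescribed errors from that field using the protocol's own criterion, for all initiators, including those with no second prescription.
3. Report the refill ratio separately as a proxy for possible excess use. Compute it only between consecutive prescriptions of the same strength, and treat an interval that ends in a change of strength as not assessable, with the number of such intervals shown.
4. Label the proxy as based on prescribing or dispensing, and not as administered doses. Reword the definition in Section 9.3 to match.
5. Add change of strength to the limitations in Section 9.9.1, and state the same interval there as in Section 9.3 (the first prescription or any current one).

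The same-strength restriction does not deal with a same-strength renewal that comes slightly early: 4 injections renewed one day early give 4/(27/7) = 1.037, which still exceeds 1. This is a further reason to call the ratio a proxy.

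The cost is a change of wording and one variable already expected in the extract. Some dosage values will be missing, some databases may support only the proxy, and the proxy denominator will be slightly smaller.
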